1. ABBREVIATIONS

AE	Adverse event
CA	Competent authority
CE	Conformité Européene
CEC	Clinical events committee
CRF	Case report form
FDAAA	Food and Drug Administration Amendments Act
GCP	Good clinical practices
ID	Identity Number
IRB	Institutional Review Board
SAE	Serious Adverse Event
SOC	Standard of Care
USADE	Unanticipated Serious Adverse Device

3. STUDY SUMMARY

Title:	Automated Ultrasound Flow Monitoring for Maturation of Peripheral Arteriovenous Fistulae
Protocol Number:	2019-1
Design:	
This is a prospective, single arm, non-randomized, multi-center observational study to demonstrate the performance of the EchoMark and EchoSure devices in patients undergoing peripheral arteriovenous fistula creation for hemodialysis access.
 
Stage 1: EchoMark implantation at the time of fistula creation with scheduled follow up for EchoSure imaging of the fistula maturation process. This stage will produce EchoSure criteria for early prediction of maturation failure.
 
Stage 2: EchoMark implantation and imaging with EchoSure to prove the robustness of the fistula maturation failure criteria established in stage 1 and measure the effect on ultimate fistula maturation rates.

Study Duration:	
Projected enrollment of first patient: May 2020
 
Projected exit of final patient: December 2021

Primary Objective:	
Stage 1: The primary objective of the study is to collect data to verify the technology's performance in monitoring fistula maturation and understand the natural history of AV fistula flow physiology.
 
Stage 2: The primary objective of the study is to assess the ability of the EchoMark and EchoSure system to reduce the rate of failed fistula maturation.

Patient Population:	Patients undergoing upper extremity autologous arteriovenous fistula creation.
Sample Size:	
Stage 1: Up to sixty (60) patients will be enrolled.
 
Stage 2: Up to sixty (60) patients will be enrolled.

Number of Sites:	To be determined
Treatments:	
Stage 1: EchoMark soft tissue marking devices will be placed and monitored using the EchoSure system for 24 weeks or confirmed fistula maturation/failure has been declared by the attending vascular surgeon, whichever comes first.
 
Stage 1: EchoMark soft tissue marking devices will be placed and monitored using the EchoSure system for up to 52 weeks. Upon the decision by the attending surgeon that the fistula failure is confirmed or that monitoring is no longer clinically necessary patients will exit the study

Endpoints:	
Stage 1:
 
• Data collection to verify accuracy• Data collection to understand the natural history of flow physiology in AV fistulas and classify fistulas that will fail 
Stage 2:
 
Primary Performance Endpoints:
 
• Rate of successful fistula maturation 
Secondary Performance Endpoints:
 
• Cumulative fistula patency at the end of 1 year• Conduit diameter measurements• Volumetric flow measurements
-------------------	--

Inclusion Criteria	
 • Age > 18 years • Patients presenting for upper extremity autologous arteriovenous fistula creation for hemodialysis access where the surgeon selects EchoMark and EchoSure as an appropriate method of monitoring. • Patient is able to sign informed consent and able to participate in all testing associated with this clinical investigation • Women of childbearing potential have a negative pregnancy test.
Exclusion Criteria	
 • Age <18 years old • Patient unable to sign informed consent • Patient participating in another investigational device or pharmacological study • Prisoner or patient from vulnerable populations as defined in 45 CFR 46.
Follow Up:	Patients will have variable follow up depending on the rate of fistula maturation as well as the follow up required by the surgeon per his or her standard practice.

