Hemodialysis access is a conduit through which dialysis machinery may be connected to the patient's circulatory system. The creation and maintenance of access constitutes a significant portion of dialysis costs. A fifth of all ESRD hospitalizations are attributable to access complications. Current clinical practice guidelines maintain that an autogenous arteriovenous (AV) fistula is the ideal vascular access conduit for hemodialysis (Figure 1).(6) Fistulae are superior to prosthetic grafts insofar as they require fewer interventions to maintain patency, have a far lower rate of failure and infection and a longer usable lifespan. Indwelling central venous catheters have the highest risk of death, infection and cardiovascular morbidity.(7) Autogenous AV fistulae confer a mortality benefit when used for dialysis.(1) In the United States, 63% of patients on dialysis use fistulae.(6)

The primary limitation of AV fistulae is the high rate of failure. Between 30%-70% of fistulae suffer primary failure and are never used because they have failed to mature or adapt into suitable dialysis access.(1) This failure nearly always results in a delay in dialysis initiation and requires placement of a dialysis catheter in addition to another surgery for access creation. The financial burden of a failure to mature is accordingly substantial. Dialysis-related expenses incurred by patients in their first year of renal failure are 23% lower if dialysis is started in a mature fistula than without.(8) Techniques to maximize the rates of maturation hold substantial potential for cost savings. Muray-Cases et al. demonstrated that a program of pre-maturation ultrasonography and intervention resulted in a maturation success rate of 78% at the time of dialysis.(9) Notably, the study involved exclusively distal radiocephalic fistulas, a type that has a typical historical rate of maturation failure between 50-70%.(10) Currently, resource limitations enable reimbursed performance of a Duplex ultrasound if maturation is not present at six weeks. Ultrasound surveillance of the maturing fistula in the early postoperative period is not typically performed as CMS and local coverage determination criteria require clinical indications that cannot apply in the early postoperative period. This 'blind period' immediately after fistula creation holds substantial potential for improvement of care.

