While we have described a 50% decrease in maturation failure as reasonable, at least one study of early postoperative ultrasound for maturation monitoring has shown results surpassing this figure. Muray Cases et al. used early ultrasonography to achieve a 78% maturation success rate. In almost all cases of incipient maturation failure, a single, correctible lesion was identified.(9) Remarkably, because of this early detection not a single patient initiated dialysis with a central venous catheter.(9)

Despite the obvious benefit of ultrasonography to reduce maturation failure, regular surveillance imaging of dialysis access is not routinely performed in the United States. Because of the onerous requirements for high trained technical staff, an interpreting physician, a fully equipped and certified vascular laboratory and the time and effort required to undergo formal ultrasound examination, responsible resource utilization precludes frequent formal scanning. In fact, meeting Medicare criteria for medical necessity for such imaging after the maturation study at six weeks requires documentation of quantifiable access malfunction occurring during dialysis or major clinical findings such as massive upper extremity swelling. This limitation is understandable in light of the economic burden associated with a lengthy Duplex examination of hemodialysis access. Ultrasound assessment of dialysis access entails the cost of a dedicated vascular laboratory, an ultrasound apparatus and a qualified ultrasound technologist. A full examination uses color Doppler imaging, pulsed-wave spectral Doppler imaging, and B-mode ultrasound. The patient burden is equally involved, requiring a separate appointment on an additional delay at a vascular laboratory that may be distant from the patient's dialysis center. The study yields a comprehensive assessment of the fistula and the potential to diagnose conditions ranging from aneurysmal degeneration to medial calcinosis and peripheral ischemia.

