5. STUDY OBJECTIVES

Purpose

Stage 1: The primary objective of Stage 1 of the study is to collect data to verify the technology's performance in fistula monitoring. In Stage 1, EchoMark is implanted and monitoring is completed post-operatively. EchoSure data is then captured in an effort to establish normal ranges of the relevant variables in the context of appropriately maturing fistulae and their physiology, which is currently unknown.

Stage 2: The purpose of Stage 2 of the study is to evaluate the performance of the EchoMark and EchoSure (both FDA approved devices) as an ultrasound-based method of monitoring maturation of fistulae. The implant and ultrasound will be used as per IFU. The primary purpose of the study is to collect data on patient outcomes and assess whether or not the information generated from use of

EchoMark and EchoSure can decrease the fistula maturation failure rate and improve the patency of fistulas after up to a year.

Performance Goals

Stage 1:

Primary Performance Endpoint:

- Data collection to verify accuracy
- Data collection to understand the natural history of flow physiology in AV fistulas and classify fistulas that will fail

Primary Safety Endpoint:

- Procedure freedom from Serious Adverse Events (SAEs) during the EchoMark implantation procedure and subsequent post-operative period

Stage 2:

Primary Performance Endpoint:

- Failed fistula maturation rate

Secondary Performance Endpoints:

- Cumulative fistula patency at the end of 1 year
- Volumetric flow data
- Vessel caliber
- Total cost of episode of care

Primary Safety Endpoint:

- Procedure freedom from Serious Adverse Events (SAEs) during the EchoMark implantation procedure and subsequent post-operative care.

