7. STUDY POPULATION

Number of Patients

Stage 1: Up to sixty (60) patients will be enrolled and both men and women will

be eligible for inclusion. The estimated enrollment period is six months and patients will be followed until the fistula matures and is suitable for use in dialysis or it is ultimately considered non-salvageable by the vascular surgeon.

Stage 2: Up to sixty (60) patients will be enrolled and both men and women will be eligible for inclusion. The estimated enrollment period is twelve months and patients will be followed until then or the decision by the attending surgeon that the fistula failure is confirmed, or that monitoring is no longer clinically necessary patients will exit the study.

Intended Use

The EchoMark and EchoSure devices are intended to be used by a trained medical professional. The EchoMark device is intended to be a Single Use Device, used in a surgical operating suite or equivalent setting. The EchoSure ultrasound devices are reusable and may be used in the operating suite, a post-operative unit such as the ICU or patient floor, or a typical outpatient clinic. When used intraoperatively or in the presence of breached skin, the ultrasound transducer should be used with a sterile probe cover.

Inclusion Criteria

- Age > 18 years
- Patients presenting for upper extremity arteriovenous fistula construction with autologous tissue for the purpose of eventual hemodialysis access where the surgeon has selected EchoMark and EchoSure as the optimal method of vascular monitoring based on clinical assessment and plan
- Patient is able to sign informed consent and able to participate in all testing associated with this clinical investigation
- Women of childbearing potential have a negative pregnancy test

Exclusion Criteria

- Age <18 years old
- Patient unable to sign informed consent
- Patient participating in another investigational device or pharmacological study
- Prisoner or patient from vulnerable populations as defined in 45 CFR 46.

This study will not target the recruitment of any potentially vulnerable subjects. If vulnerable subjects who are educationally or economically impaired present for fistula creation, they will not be given the opportunity to participate in the study.

PATIENT WITHDRAWAL FROM THE STUDY

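### The Stage 1 versus Stage 2 maturation test has no common scoring time, no stated definition of success and no rule for unresolved fistulas, and the stated observation windows differ and conflict

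*Combined protocol and SAP*

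**What the plan says.** **Endpoint and test.** Section 5 names the Stage 2 primary performance endpoint as "Failed fistula maturation rate"; the Study Summary (Section 3) names it as a success rate. Neither gives a criterion or a time. Section 8 (Stage 2) tests it by chi-square between the Stage 1 and Stage 2 cohorts. The same section separates unassisted from assisted maturation when it describes the association coefficients, but does not say which of them the chi-square counts. Part of Section 8 is redacted; the visible endpoint, test and follow-up sentences are complete.

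**Observation windows.**
- Study Summary, Treatments: Stage 1 is "monitored using the EchoSure system for 24 weeks or confirmed fistula maturation/failure has been declared by the attending vascular surgeon", whichever comes first. The next row, again labelled Stage 1, is "monitored using the EchoSure system for up to 52 weeks". The one-year patency endpoint and the one-year stop in Section 10 show that Stage 2 is meant.
- Study Summary, Follow Up: "Patients will have variable follow up depending on the rate of fistula maturation".
- Section 7, Stage 1: "The estimated enrollment period is six months and patients will be followed until the fistula matures and is suitable for use in dialysis", or until the surgeon considers the fistula beyond salvage. There is no 24-week limit. For Stage 2 the end point is worded unclearly, as the end of a twelve-month period or a surgeon's decision.
- Section 10, Stage 1: until the fistula has matured and dialysis through it has begun, or failure is declared, again with no cap. Stage 2 ends at one year if the fistula is functioning, at declared failure, or when monitoring is no longer needed.

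**Forms.** The Section 10 schedule places the End of Trial Period Form only at the start of dialysis or at fistula failure.

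**The concern.** A comparison of two proportions needs the same event, counted over the same period, in both groups. Here the period may be 24 weeks in one cohort and 52 in the other, or open-ended in the first and about a year in the second, depending on which section is followed. A patient whose fistula is neither mature nor failed when observation ends has no assigned outcome. Two analysts could therefore compute different primary results from the same patients and both claim to follow the plan. Under one plausible set of choices, longer observation alone would raise the Stage 2 rate and could be read as a device benefit.

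**Working it through.** **1. The plan's own figure.** Inputs from Section 8: success 50% versus 78%, alpha 0.05 (two-sided assumed), power 80% (the plan's beta = 0.8 read as power), 25% dropout. With mean rate 0.64:

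n = [1.960 × √(2 × 0.64 × 0.36) + 0.842 × √(0.50 × 0.50 + 0.78 × 0.22)]² / 0.28² = (1.330 + 0.546)² / 0.0784 = 44.9, so 45 per stage; 45 / 0.75 = 60.

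The stated 45 and 60 reproduce. The sample size arithmetic is sound; what is missing is the time and definition to which the two rates apply.

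**2. Unequal windows under one reading.** Assume that (a) the Summary's 24 and 52 weeks govern outcome ascertainment, (b) Stage 1 fistulas unresolved at week 24 count as not matured, (c) the device has no effect and 50% are mature by week 24. A share d maturing after week 24 then counts only in Stage 2, so Stage 1 is scored at 50% and Stage 2 at 50% + d. The documents give no value for d; 2, 5 and 10 points are assumptions. The table gives the exact probability that the uncorrected two-sided 5% chi-square is significant in favour of Stage 2, summed over all pairs of binomial counts.

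| d | 45 per stage | 60 per stage |
|---|---|---|
| 0 | 2.3% | 2.7% |
| 2 points | 3.5% | 4.4% |
| 5 points | 6.3% | 8.5% |
| 10 points | 14.8% | 20.4% |

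**3. The same situation under another convention.** Drop (b) and leave unresolved Stage 1 fistulas out of the denominator. Illustrative assumptions: 50% mature and 20% unresolved at week 24, half of the unresolved maturing later and the rest counted as not matured in Stage 2.
- Stage 1: 50 / 80 = 62.5%, on 45 × 0.80 = 36 patients.
- Stage 2: 50 + 10 = 60%, on 45 patients.
- Chance of a false finding for Stage 2: 1.4%, against 14.8% for the same 10-point late gain in step 2.

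With 10% unresolved the rates are 50 / 90 = 55.6% and 55%, nearly equal. The counting rule alone decides whether there is a bias and which way it runs.

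**4. Planning rates.** Section 4 gives the 78% benchmark as "resulted in a maturation success rate of 78% at the time of dialysis", while Section 8 powers on failure in an undefined early postoperative period. Exact power for 50% versus 78% is 80.9% at 45 per stage and 90.3% at 60. If both rates are 5 or 10 points lower at the common time, it is 77.6% or 75.8% at 45 (88.9% or 88.5% at 60). If only the 78% is 5 or 10 points lower, it is 61.8% or 40.5% at 45 (74.5% or 52.7% at 60). These shifts are assumptions too.

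**5. Calendar.** The Summary projects a first patient in May 2020 and "Projected exit of final patient: December 2021", at most 20 months. Section 7 estimates six plus twelve months of enrolment. In the best case Stage 2 enrols from 1 November 2020 to 31 October 2021, which leaves its last patient 61 days (8.7 weeks) before 31 December 2021. With even enrolment, those entering in the last 107 of 365 days (29.3%) would have under 24 weeks.

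**The case against.** A reader might infer that the plan is biased in favour of Stage 2. The documents do not support that. The Summary's 24 weeks is a duration of EchoSure monitoring, and it does not say that outcome ascertainment stops then; Sections 7 and 10 continue it. Even if it does stop, step 3 shows that the direction depends on a counting rule that the plan does not state. This objection stands, and the table in step 2 describes one reading only.

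A second objection is that the Summary speaks of the effect on ultimate maturation, and that Sections 7 and 10 with variable follow-up describe an event-driven endpoint, for which a fixed week is not the only valid repair. This also stands in part: a common time replaces ultimate maturation with a different quantity, and that must be said openly. It does not rescue the plan, because a 24-week cap on one cohort and a one-year stop on the other do not give the same chance of reaching a resolved outcome.

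Third, the exit events in Sections 7 (suitable for dialysis) and 10 (dialysis begun through the fistula) might be read as rival endpoint definitions. They are rules for leaving follow-up, and Section 10 treats maturation and the start of dialysis as separate conditions. The clearer definitional gap is the assisted/unassisted split in Section 8.

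Fourth, Section 11 requires the exit date, whether the patient completed the trial, and the reason for any discontinuation. Unresolved exits are therefore recorded, although no rule scores them.

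Finally, the background mentions "such imaging after the maturation study at six weeks requires documentation", and Section 8 has six-week correlations. The former describes usual practice and the latter concern flow and diameter; neither sets a scoring time for the primary test.

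**Conclusion.** The gap is real under every reading: the between-stage test has no scoring time, no rule for unresolved fistulas and no statement on assisted maturation, and the follow-up passages conflict. It should be closed before the stages are compared.

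The size of any bias is not established. It is negligible at 1 to 2 points of late maturation and material from about 5, but only if the Summary governs ascertainment and unresolved Stage 1 fistulas count as not matured. If Sections 7 and 10 govern, a bias against Stage 2 would need early Stage 2 exits or Stage 1 maturation after about a year.

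A longer Stage 2 window for one-year patency is not in itself a defect, and the projected dates are not a stopping rule; they only limit which common time is feasible.

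**What to change.** - Reconcile the follow-up statements in the Study Summary (Treatments and Follow Up), Section 7 and Section 10, and correct the second Treatments label.
- For the between-stage test only, score maturation in both stages by one written definition that says whether assisted maturation counts, at one common time after fistula creation lying within both windows (so not later than week 24 if the Summary is confirmed).
- Count fistulas not mature by then as not matured. State in advance how patients who leave earlier without a declared outcome are counted; Section 7 already removes the data of those who withdraw.
- State that this measures maturation by that time, not ultimate maturation. If ultimate maturation is kept, give both stages the same maximum follow-up and the same rule for unresolved fistulas.
- Confirm that the 50% and 78% apply to the chosen definition and time, or restate the power. Check that every Stage 2 patient can reach that time under the projected dates.

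Later Stage 2 data still serve one-year patency, and monitoring and clinical decisions do not change.

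**Cost.** Protocol and SAP wording and one maturation status field. Because no visit is fixed at a set week, a chart check or contact may be needed, and the projected dates may have to move. Stage 2 fistulas maturing after the common time would not count in this test, and the stated power may fall. Confounding between sequential, non-randomised cohorts remains.

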6. STUDY DESIGN

This is a prospective, single arm, non-randomized, multi-center observational study to record objective data in patients undergoing upper extremity arteriovenous fistula construction with autologous tissue for the purpose of eventual hemodialysis access, in whom the EchoMark implantable marker is placed at the site of vascular anastomosis and the EchoSure module is used to collect ultrasonic data.

The expected duration of this study will be from May 2020 to December 2021. Patients will be identified and recruited by the surgeons participating in the study, who will be determined at a later date. Patients who have been scheduled for creation of an upper extremity autologous arteriovenous fistula creation surgery will be identified as appropriate for study recruitment. The study details will be explained to identified patients and the consent process will begin for willing patients. Participants in the study will have EchoMark devices implanted at the time of the surgery. Monitoring of fistulae will be performed in the postoperative period. Patients who wish to terminate their participation in the research will no longer receive EchoSure ultrasound examinations of their fistula and will revert to the standard monitoring practice of their surgeon.

Stage 1: Patients will be monitored using the EchoSure ultrasound to collect data. Data will be analyzed in an attempt to formulate normative ranges for relevant variables such that clear, objective metrics consistent with healthy versus pathologic fistula healing are established.

Stage 2: Patients will be monitored via EchoSure ultrasound in addition to the standard of care currently followed by the surgeon. Decisions will be made by the vascular surgeon, using a combination of clinical data and the EchoSure data to determine if and when interventions need to be made to prevent failure of fistula maturation. We will then calculate the effect of the EchoMark and EchoSure on the rate of successful fistula maturation.

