For this portion of the study, we will recruit an additional 60 patients planning to undergo elective construction of upper extremity autogenous hemodialysis access. Again, the EchoMark fiducial marker will be inset at the time of fistula creation. The minimum sample size of 45 (60 prior to 25% dropout factor) is powered to detect an approximate 25% reduction in all-cause fistula failure in the early postoperative period. A χ^2 power analysis was performed with $\alpha = 0.05$, $\beta = 0.8$ and standard-of-care fistula maturation success at 50% based on institutional experience and prior literature which ranges from 30-70% and EchoSure early intervention success based on the Muray-Cases results which showed a 78% success rate achieved by a novel program of pre-maturation ultrasonography and early intervention.

The nominal-by-interval association coefficient, Eta, will be calculated to determine the correlation between successful, unassisted maturation and EchoSure-derived values for flow and conduit diameter at two weeks. This will be compared to the similar findings of stage 1 using Student's t-testing and will validate the early maturation criteria derived from there. The association coefficient will be calculated to determine the correlation between successful, assisted maturation and EchoSure-derived values for flow and conduit diameter immediately following intervention. Pearson's correlation will be performed on both EchoSure-derived and Duplex-derived values of volumetric flow and conduit diameter to determine correlation between findings immediately following intervention and those at six weeks. [REDACTED]

Using χ^2 testing between the stage 1 and 2 cohorts, the benefit to maturation success of intervention based on early postoperative EchoSure examination will be determined.

9: PATIENT ENROLLMENT AND CONSENT

Method of Subject Identification and Recruitment

Patients will be identified and recruited by the surgeons participating in the study. Patients who have been scheduled for a fistula creation surgery will be identified as appropriate for study recruitment. The study details will be explained to identified patients and the consent process will begin for willing patients.

Informed Consent

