10. STUDY PROCEDURES AND METHODS

Patients undergoing fistula creation procedures will be identified. The study will be explained to these patients and informed consent for participation in the study will be obtained from willing patients. A small, FDA-approved tissue marker will be implanted prior to closure of wounds following the Instructions for Use on the FDA-approved labelling.

Stage 1: The fistula will be assessed with intermittent EchoSure examinations, sometimes during routine dialysis visits (maximum 3x/week) to minimize travel. This will conclude when the fistula has entirely matured and the patient begins hemodialysis via the fistula or when the vascular surgeon declares that the fistula has failed despite any and all salvage attempts.

Stage 2: Similar to stage 1 but with implementation of the normative values for relevant variables that resulted from the data collected in stage 1, with subsequent use of the EchoSure flow information in the vascular surgeon's decision making. This stage will also conclude when a year has passed and the fistula is functioning or when the vascular surgeon declares that the fistula has failed despite any and all salvage attempts or that monitoring is no longer clinically necessary.

Actions to Be Taken by Site Staff	Screening and pre-operative evaluation	Clinic Visits	Initiation of dialysis or fistula failure
Consenting	X		
Initial Enrollment Form		X	
Nurse Scan Form		X	
EchoSure Scan		X	
Standard Clinical Exam		X	
End of Trial Period Form			X

11: DATA COLLECTION, ANALYSIS, AND MONITORING

Adverse events are not expected in this study. Unanticipated problems will be reported and discussed with the principal investigator and research coordinator. Patients will be regularly monitored for signs of infection, inflammation or device extrusion. Should the implantable device require removal, it will be removed, and patient will be monitored with conventional methods. The research team will periodically review its protocols to ensure maximal patient safety and data validity.

Source Documentation

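### The Stage 2 maturation endpoint has no scoring rule, and nothing keeps EchoSure readings out of the surgeon's outcome call in one of the two cohorts compared

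*Combined protocol and SAP*

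**What the plan says.** **Endpoint.** The Study Summary (section 3) gives the Stage 2 primary endpoint as "Rate of successful fistula maturation". Study Objectives (section 5) gives "Failed fistula maturation rate". Neither adds a criterion, an assessment time or an assessor. Section 8 distinguishes assisted from unassisted maturation but does not say whether both count as success.

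**Exit rules, the only operational text.**
- Section 3, Treatments, Stage 1: monitoring ends at 24 weeks or when "confirmed fistula maturation/failure has been declared by the attending vascular surgeon, whichever comes first". The next line covers up to 52 weeks; it is also labelled Stage 1 but evidently means Stage 2. There the surgeon confirms failure or decides that monitoring is no longer needed.
- Section 7, Stage 1: follow-up ends when the fistula is fit for dialysis use or the surgeon considers it beyond salvage. Stage 2 again refers to the surgeon's decision on failure or on the need for monitoring.
- Section 10, Stage 1: "This will conclude when the fistula has entirely matured and the patient begins hemodialysis via the fistula", or when the surgeon declares failure. Stage 2: "This stage will also conclude when a year has passed and the fistula is functioning", or on surgeon-declared failure, or when monitoring is no longer needed.
- The section 10 schedule, which is not split by stage, has a column for the start of dialysis or fistula failure, at which the End of Trial Period Form is completed.

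**What the surgeon knows.** Section 6 says of Stage 2: "Decisions will be made by the vascular surgeon, using a combination of clinical data and the EchoSure data". The sentence goes on to say that these decisions concern whether and when to intervene. Section 10 adds that the Stage 1 normative values are put to use in Stage 2.

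**Comparison.** Section 8 applies a chi-square test to the two stages, by which "the benefit to maturation success of intervention based on early postoperative EchoSure examination will be determined".

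**The concern.** With no endpoint definition, a site or analyst would have to score success and failure from the exit rules, and these rest largely on an unblinded treating surgeon. In Stage 2 that surgeon holds device readings and reference ranges with a directed use; in Stage 1 the reference ranges do not yet exist. If they colour the outcome call, a borderline fistula with reassuring flow may be counted as mature, or one with low flow may be declared failed sooner. Either would move the Stage 2 rate without any change in the fistulas, and section 8 would credit the movement to EchoSure-based intervention. More patients would not remove a bias of this kind. No blinded or independent outcome assessment is described; a clinical events committee appears only in the abbreviation list.

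**Working it through.** **1. Reproduce the plan's sample size.** Inputs from section 8, Stage 2: success 50% under standard care and 78% in Stage 2, alpha 0.05, power 0.80 (printed as beta = 0.8), 25% dropout. Sidedness is not stated; two-sided without continuity correction reproduces the figure. With mean rate (0.50 + 0.78)/2 = 0.64:

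n = [1.960 × √(2 × 0.64 × 0.36) + 0.842 × √(0.50 × 0.50 + 0.78 × 0.22)]² / 0.28² = 44.9, so 45 per stage.

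45 / 0.75 = 60 enrolled. Both figures match the plan. The concern disputes neither.

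**2. Set the rules side by side.**

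| Outcome | Stage 1 | Stage 2 |
|---|---|---|
| Maturation | Surgeon's declaration (section 3); fit for dialysis use (section 7); dialysis via the fistula (section 10) | No declarant named; functioning at one year (section 10) |
| Failure | Surgeon's call | Surgeon's call |
| Stage 1 norms in use | No, not yet derived | Yes (section 10) |
| EchoSure scans done | Yes | Yes, with directed use in decisions (sections 6 and 10) |

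The documented difference between the stages is therefore the norms and the directed use of readings. Whether these also reach the outcome call is not written; no text prevents it.

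**3. Illustrate the size.** Assumptions, none from the documents: 45 evaluable per stage, true maturation 50% in both, and a net k of 45 Stage 2 fistulas scored differently because of EchoSure, so that the scored Stage 2 rate is 0.50 + k/45. The probability of a significant result favouring Stage 2 is summed exactly over the two binomial distributions, using the uncorrected chi-square test at two-sided 5%.

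| Net k | Scored Stage 2 rate | Chance of a significant Stage 2 benefit |
|---|---|---|
| −2 | 45.6% | 0.8% |
| 0 | 50.0% | 2.3% |
| +2 | 54.4% | 5.7% |
| +3 | 56.7% | 8.5% |
| +5 | 61.1% | 17.4% |

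With 60 per stage and the same scored rates, k = 0 gives 2.7% and the rate for k = +5 gives 24.0%, so enlarging the study raises the error. With k = +5 and 45 per stage, true rates of 30% and 70% (the ends of the range quoted in section 8) give 20% and 24%.

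**4. The opposite direction.** At the planned 50% versus 78%, exact power with 45 per stage is 81%. If a net 3 of 45 Stage 2 successes are scored as failures, the scored rate is 0.78 − 3/45 = 71.3% and power is 55%. For a net 5 it is 66.9% and 36%.

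**The case against.** The strongest reply is that the plan never says the outcome is the surgeon's opinion.

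- The section 3 sentence on declared maturation or failure is a Stage 1 rule for ending monitoring. It is not an endpoint definition. This stands: a reader might infer that maturation in Stage 2 is whatever the attending surgeon declares, but no text says so.
- Section 6 ties EchoSure data to intervention decisions, which is how the device is meant to work. A reader might take the sentence as evidence that readings decide the outcome call; read to its end, it does not say that. Influence on scoring remains an inference, from the same person making both judgements with no barrier between them.
- A reader might infer that Stage 2 surgeons differ in having chosen the device or knowing the cohort. Choosing the device is an inclusion criterion in both stages, surgeons know the cohort in both, and Stage 1 surgeons are not stated to be blind to the scans.
- Section 10 already names an observable event, and its schedule applies to both stages. That is correct, and the remedy builds on it, but neither endpoint list nor section 8 adopts it as the endpoint.
- Upgrades and downgrades may cancel: 5 up and 3 down is net +2 (5.7%), and net zero leaves 2.3%. Hence the net counts above.
- Section 8 has a redaction just before the chi-square sentence, and the End of Trial Period Form is not shown. Either could hold outcome criteria, so the statement is limited to the visible text.

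**Conclusion.** The concern holds as a gap in the visible plan. The Stage 2 primary endpoint has no scoring criterion, failure is the unblinded treating surgeon's call in both stages, and nothing excludes EchoSure values from that call in the stage where the surgeon is told to use them. The documents do not support saying that scoring is biased, or that any bias must favour the device.

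Its size depends on assumed net counts. At 45 per stage and 50% true maturation in both, the chance of a false Stage 2 benefit moves from 2.3% to 5.7% at net +2 and to about 17% at net +5, and falls to 0.8% at net −2. At the planned effect, a net loss of 3 successes takes power from 81% to 55%. The matter bears on the main comparison and is cheap to prevent, so the plan should be changed.

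**What to change.** In sections 3, 5 and 8, define the chi-square endpoint identically for both stages:

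1. **Success** is documented dialysis through the study fistula by one common time point, stated in advance. This is the event in section 10's Stage 1 rule and schedule. Record it with its date on the End of Trial Period Form, from dialysis records.
2. **Patients not yet on dialysis by then** are classified by one pre-stated rule based on the standard clinical exam that both stages already have. EchoSure values are excluded. Duplex scans should not be relied on, because Stage 2 readings may prompt them and so make them selectively available.
3. **State whether assisted maturation counts as success.**
4. **Report the surgeon's declaration as a secondary outcome.**

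This concerns scoring only and changes no one's care.

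The cost is protocol and SAP wording plus retrieval of dialysis records, which may sit outside the study site. For Stage 1 patients whose monitoring ends on a declaration of maturation, the records may have to be sought after exit. Some fistulas will be classified differently from the surgeon's own view. The change reduces the bias but does not abolish it: the surgeon can still influence when the fistula is first used, and an examiner may know the readings. Both should be stated as limitations.
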